6.2.1.5 Dosage Adjustments, Delays, Rules for Withholding or Restarting, Permanent Discontinuation

Dosage Adjustments

The subject should continue on the same dose of AMG 224 throughout the study unless the following events occur:

- For subjects experiencing an adverse event meeting the DLT definition or intolerable related adverse events BUT showing evidence of response, there will be an option to reduce the dose to the immediate next lower dose level (ie Dose Level -1 as outlined in [Table 3](#) or a further lower dose level (ie Dose Level -2 as outlined in [Table 3](#)).
- The study drug can be resumed once the adverse events recover to baseline or Grade 1 and the reintroduction of AMG 224 is deemed safe by the Investigator, Amgen's Medical Monitor, and Global Safety Officer.
- Subjects must be informed of the risk of continuing on therapy. Each subject is only allowed a single dose reduction.
- For subjects experiencing thrombocytopenia after the DLT-window, there will be an option to reduce the dose to the immediate next lower dose level (ie, Dose Level -1 as outlined in [Table 3](#)) or a further lower dose level (ie Dose Level -2 as outlined in [Table 3](#) in the dose expansion part of the study (as described in [section 6.3.1](#)).

The investigator should notify Amgen immediately before administration of the lower dose of AMG 224.

Subject who have been dose-reduced will have an option to receive the higher dose (ie, Dose Level -1 or Dose Level 1) at the next planned cycle if the adverse event resolves to \leq grade 1 or baseline and the reintroduction of AMG 224 at the higher dose is deemed safe by the Investigator.

For dose reduction level, refer to [Table 3](#):

Table 3. Dose Reduction of AMG 224 for Toxicity (Only in Dose Expansion)

Dose level	Dose IV Q3W
Dose Level 1	
Dose Level -1	
Dose Level -2	

Subjects should not be rechallenged with AMG 224 if the following AMG 224-related adverse events occur:

- Any life-threatening adverse events
- DILI (Drug Induced Liver Injury) meeting Hy's law

- Persistent grade 3 adverse events that do not recover to baseline or Grade 1 within 4 weeks. Any treatment-related adverse event meeting DLT-criteria that recurs

Dosage Delays

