6.2.1.6 Dosage Limiting Toxicities

The grading of adverse events will be based on the guidelines provided in the Common Terminology Criteria for Adverse Events (CTCAE) version 4.0 (available online at <http://evs.nci.nih.gov/ftp1/CTCAE/About.html>). Determination of the severity of adverse events will be consistent with Common Terminology Criteria for Adverse Events (CTCAE) version 4.0. The relationship of an adverse event to investigational product will be determined by the Investigator. An event should be considered related to treatment if, in the Investigator's medical judgment, there is a reasonable possibility that the event may have been caused by AMG 224.

A DLT is defined as a Grade 3 or higher non-hematological or a Grade 4 hematologic adverse event that occurs during the DLT window (day 1 through day 28 after the administration of the first dose of AMG 224) in Part 1 Dose Exploration unless clearly attributable to causes other than AMG 224 treatment. DLT toxicities do not include fatigue, nausea, diarrhea, vomiting, neutropenia, anemia, thrombocytopenia and lymphopenia, increased serum creatinine or electrolytes abnormalities that are not clinically significant and require no treatment unless the following criteria are met:

Hematological toxicity:

- Grade 4 neutropenia lasting > 7 days
- Grade 3 or 4 neutropenia with fever > 38.5°C
- Grade 3 thrombocytopenia with ≥ Grade 2 hemorrhage
- Grade 4 thrombocytopenia lasting > 7 days
- Grade 3 anemia with symptoms or required intervention (eg, transfusion)
- Grade 4 anemia
- Lymphopenia of any grade is not considered a DLT

Approved

Non-hematological toxicity:

- \geq Grade 3 nausea, vomiting or diarrhea persisting more than 3 days despite optimal medical support
- Grade 3 fatigue persisting > 7 days
- \geq Grade 3 acute kidney injury (creatinine >3 X baseline or > 4.0 mg/dL) lasting > 3 days
- Elevation of either AST or ALT according to the following criteria:
 - $> 8x$ ULN;
 - $> 5x$ ULN but $< 8x$ ULN for ≥ 2 weeks;
 - $> 5x$ ULN but $< 8x$ ULN and unable to adhere to enhanced monitoring schedule; or
 - $> 3x$ ULN with clinical signs or symptoms that is consistent with hepatitis (such as right upper quadrant pain/tenderness, fever, nausea, vomiting, jaundice, rash or eosinophilia ($> 5\%$)).
- TBIL $> 3x$ ULN

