ORR	overall response rate
PD	pharmacodynamics or progressive disease
PK	pharmacokinetics
PKDM	pharmacokinetics and data management
PT	prothrombin time
Q3W	once every 3 weeks
QD	once daily
QT	QT interval is a measure of the time between the start of the Q wave and the end of the T wave in the heart's electrical cycle as measured by ECG
QTc	QT interval corrected for heart rate using accepted methodology
QTcF	QT interval corrected for heart rate using Fridericia's formula
QD	once daily
RP2D	recommended phase 2 dose
sCR	stringent complete response
SD	standard deviation / Stable disease
SFLC	serum free light chain
SPEP	serum protein electrophoresis
T _{1/2}	half-life
t _{max}	time of maximum observed serum concentration
TPI	toxicity probability interval
TNSr	total neuropathy score-reduced
UPEP	urine protein electrophoresis
VGPR	very good partial response

1. Introduction

The purpose of this Statistical Analysis Plan (SAP) is to provide details of the statistical analyses that have been outlined within the draft protocol amendment 4 for study 20130314, AMG 224 **dated 16 July 2018**. The scope of this plan includes the primary analysis and the final analyses that are planned and will be executed by the **Amgen Global** Biostatistical Science department unless otherwise specified.

2. Objectives, Endpoints and Hypotheses

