3.1 Study Design

This is a Phase 1, first-in-human, multicenter; non-randomized, open-label, dose-exploration and dose expansion study of AMG 224 IV Q3W for subjects with relapsed or refractory multiple myeloma. The study will be conducted in two parts:

Part 1- Dose Exploration to define the MTD and / or RP2D followed by **Part 2 - Dose Expansion** to obtain further safety and efficacy data.

Eligible subjects enrolled in the study will receive AMG 224 IV once Q3W beginning at study Day 1. During the initial DLT window (Day 1 through Day 28) subjects will be assessed for DLT. DLTs are defined in protocol Section 6.2.1.6. Dosing with AMG 224 may continue Q3W unless there is evidence of progressive disease (PD) defined by IMWG, the subject becomes intolerant to the study medication, signs and symptoms of clinical progression are evident as determined by the principal investigator, or the subject withdraws consent.

Part 1 – Dose Exploration

In Part 1 for the first dose level and at each new higher dose level, the first enrolled subject will be treated, and then after a period of 24 hours, subsequent subjects will be treated, provided that there are no safety concerns relating to the treatment of the first subject.

The dose-exploration cohorts will define the preliminary MTD, safety, tolerability, PK, and PD of AMG 224. A 3+3 design will be used to make a preliminary estimate of MTD. The preliminary MTD is defined as the maximum dose at which fewer than **33% of subjects** experience a DLT. A final estimate of the MTD will be made using data from Dose Exploration and Dose Expansion. Planned dose levels for the dose-exploration cohorts are as follows: 30, [REDACTED] of AMG 224 (IV; Q3W).

Dose exploration decisions will be made by the Dose Level Review Team (DLRT). All cumulative safety and laboratory data will be reviewed prior to making dose exploration decisions. Safety data from all enrolled subjects in preceding cohorts and dose levels will also be considered. Additionally, the DLRT may stop enrolment into a cohort at any time to evaluate safety.

3+3 Design:

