Change from Baseline is the arithmetic difference between post-dose assessments and Baseline.

C_{max}

Maximum observed serum AMG 224 concentration during a treatment cycle.

C_{min}

Minimum observed serum AMG 224 concentration during a treatment cycle.

Death Date

Death Date for each subject is defined as the date collected on the End of Study CRF where the reason for ending the study is equal to Death.

Dose Limiting Toxicity (DLT):

A DLT is defined as a Grade 3 or higher non-hematological or a Grade 4 hematologic adverse event that occurs during the DLT window (day 1 through day 28 after the administration of the first dose of AMG 224) in Part 1 Dose Exploration unless clearly attributable to causes other than AMG 224 treatment. DLTs do not include fatigue, nausea, diarrhea, vomiting, neutropenia, anemia, thrombocytopenia and lymphopenia, increased serum creatinine or electrolytes abnormalities that are **not** clinical significant and require no treatment unless the following criteria are met:

Hematological toxicity:

- Grade 4 neutropenia lasting > 7 days
- Grade 3 or 4 neutropenia with fever > 38.5°C
- Grade 3 thrombocytopenia with ≥ Grade 2 hemorrhage
- Grade 4 thrombocytopenia lasting > 7 days or requiring AMG 224 dose reduction is a DLT
- Grade 3 anemia with symptoms or required intervention (eg, transfusion)

- Grade 4 anemia
- Lymphopenia of any grade is not considered a DLT

Non-hematological toxicity:

- \geq Grade 3 nausea, vomiting or diarrhea persisting more than 3 days despite optimal medical support
- Grade 3 fatigue persisting $>$ 7 days
- \geq Grade 3 acute kidney injury (creatinine >3 X baseline or $>$ 4.0 mg/dL) lasting $>$ 3 days
- **Elevation of either AST or ALT according to the following criteria:**
 - **$>$ 8x ULN;**
 - **$>$ 5x ULN but $<$ 8x ULN for \geq 2 weeks;**
 - **$>$ 5x ULN but $<$ 8x ULN and unable to adhere to enhanced monitoring schedule; or**
 - **$>$ 3x ULN with clinical signs or symptoms that is consistent with hepatitis (such as right upper quadrant pain/tenderness, fever, nausea, vomiting, jaundice, rash or eosinophilia ($>$ 5%).**
- **TBIL $>$ 3x ULN**

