9.8.1 Analyses of Pharmacokinetic or Pharmacokinetic/Pharmacodynamic Endpoints

9.8.1.1 Pharmacokinetic Endpoints

PK parameters will include, but are not limited to maximum observed concentration (C_{max}), minimum observed concentration (C_{min}) and area under the concentration-time curve over the dosing interval [AUC] and if feasible half-life ($t_{1/2}$).

The PK parameters of AMG 224 conjugated antibody, Total anti-BCMA antibody, and DM1 will be estimated using standard noncompartmental methods and summarized by dose level using means, standard deviations, medians, minimums and maximums.

Serum concentrations below the lower limit of quantifications will be set to zero for the estimation of the pharmacokinetic parameters for each subject and for the calculation of the summary statistic for each time point. Actual dosing and sampling time will be used for all calculations. The reasons for excluding any sample from the analyses will be provided.

Individual concentration-time data will be summarized by dose level. AMG 224 conjugated antibody, Total anti-BCMA antibody, and DM1 concentrations at each time point along with PK parameter values may be listed for each subject. Individual concentration-time data will be tabulated and presented graphically. Summary statistics will be computed for each sampling time and parameter as appropriate.

Analysis of the relationship between AMG 224 dose and exposure parameters (AUC and C_{max}) will be conducted and plots of the relationship between AMG 224 dose and exposure parameters along with dose proportionality assessment will be provided.

Analysis of the relationship between AMG 224 conjugated antibody concentrations and change from baseline in QTcF will be conducted and plots of the relationship between AMG 224 conjugated antibody concentrations and change from baseline in QTcF will be

provided. The above analysis will also be conducted for the Total anti-BCMA antibody, and DM1.

Additional analyses to explore relationship between exposure and safety and exposure and efficacy may also be performed.

10. Changes From Protocol-specified Analyses

There are no changes to the protocol-specified analyses.

11. Literature Citations / References

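### SAP Section 5 counts grade 4 thrombocytopenia that leads to a dose reduction as a DLT; current protocol Section 6.2.1.6 does not, and the two need reconciling

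*SAP*

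**What the plan says.** Protocol Section 6.2.1.6, as it now stands, gives this hematological criterion: "Grade 4 thrombocytopenia lasting > 7 days". The corresponding bullet in SAP Section 5 (Definitions, Dose Limiting Toxicity) reads: "Grade 4 thrombocytopenia lasting > 7 days or requiring AMG 224 dose reduction is a DLT".

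Three other statements in the SAP bear on which text governs:

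- Section 1 describes the SAP as detailing the "statistical analyses that have been outlined within the draft protocol amendment 4", dated 16 July 2018.
- Section 3.1 states: "DLTs are defined in protocol Section 6.2.1.6".
- Section 10 states: "There are no changes to the protocol-specified analyses".

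DLT incidence is a primary endpoint in both documents (protocol Section 10.1.1, SAP Section 2.1). It feeds the 3+3 rules in Table 1 and the Bayesian TPI model for the final MTD (protocol Section 10.4.2.3, SAP Section 9.6.1.2).

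**The concern.** The SAP gives two answers to one question. Someone who follows its cross-reference in Section 3.1 applies the protocol criterion. Someone who follows the definition written out in Section 5 applies a wider one. Nothing in the SAP ranks the two, and Section 10 does not declare a difference.

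At stake is how a primary endpoint is classified, for the toxicity that the protocol itself calls its primary safety concern (Section 2.4.2). The amendment 4 rationale reports that grade 4 thrombocytopenia had been seen above a redacted dose. It does not say how long those falls lasted, when they occurred or whether doses were reduced. The amendment log also lists a deletion in this bullet under amendment 4. The log is used here only for timing: subjects whose DLT window closed before amendment 4 may have been judged under the longer wording, and later subjects under the shorter one. The documents do not say which list was applied to whom.

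**Working it through.** **1. The plan's own figures.** The sample-size text (protocol Section 10.2, SAP Section 3.2) gives the chance of at least one DLT at true rates of 10% and 33%. The formula is 1 − (1 − p)^n.

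- n = 3: 1 − 0.90³ = 27.1% and 1 − 0.67³ = 69.9%. The plan states 27 to 70%.
- n = 6: 1 − 0.90⁶ = 46.9% and 1 − 0.67⁶ = 91.0%. The plan states 47 to 91%.

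These reproduce, and reconciling the definitions changes none of them.

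**2. Comparison of the lists.** Taken item by item, the remaining hematological criteria and the non-hematological criteria match. The dose-reduction limb is the only substantive difference.

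**3. Which events fall between the two bullets.**

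| Grade 4 platelet fall in the DLT window | Protocol bullet | SAP bullet |
|---|---|---|
| More than 7 days | met | met |
| 7 days or less, dose not reduced | not met | not met |
| 7 days or less, dose reduced | not met | met |

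Only the last row differs.

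**4. How a subject could reach that row.** The window is Days 1 to 28 and the second dose falls on Day 22, so a decision on the second dose is normally made inside the window. The routes to a reduction are narrow, however:

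- Protocol Section 6.2.1.5 places the specific option later: "For subjects experiencing thrombocytopenia after the DLT-window, there will be an option to reduce the dose".
- The other route in that section is for events meeting the DLT definition, or for "intolerable related adverse events BUT showing evidence of response, there will be an option to reduce the dose". A short fall does not meet the protocol bullet, so what mainly remains is an intolerable related event in a subject who is responding.
- Table 3, which sets the reduction levels, applies only in dose expansion, whereas both DLT definitions are worded for Part 1.
- Table 4, the platelet-based dosing guide, is headed as applying after the second cycle.

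Few subjects can therefore be affected. The documents report none.

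**5. Scale, from Table 1 alone.** In a cohort of six, 1/6 = 16.7% leads to escalation. One further DLT gives 2/6 = 33.3%, which leads to de-escalation and is not below 33%. This shows what one reclassified subject could do under the decision table. It does not show that such a subject exists.

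**The case against.** The strongest reply is that this is leftover text rather than a choice of analysis. The SAP names the governing section, cites a draft of amendment 4 that the reader cannot see, and does not itself control dosing decisions. Those belong to the dose level review team under the protocol, and the expansion dose is already described as derived from a preliminary MTD. Most of this stands. Retained wording is the likeliest explanation, and a reader should not infer that the sponsor set out to widen the criterion. The explanation does not remove the conflict: the SAP restates a different rule in its own definitions section, and the DLT analysis and TPI model are run under the SAP.

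A second reply is that the shared lead-in may narrow the gap. It excludes a list of toxicities, thrombocytopenia among them, ending in "electrolytes abnormalities that are not clinically significant and require no treatment unless the following criteria are met". If the qualifier about clinical significance and treatment reaches back to thrombocytopenia, some short grade 4 falls could be DLTs under both documents. That is possible, but the sentence does not settle it.

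A third reply is that protocol Section 2.4.2 rules out affected subjects at the expansion dose. A reader might infer that from its remark on platelet decreases in the DLT evaluation period. The remark is a preliminary summary judgement at a redacted dose, not a count of events, so it establishes neither presence nor absence.

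**Conclusion.** The mismatch is certain on the current texts and is undeclared. It should be fixed because it concerns the definition of a primary endpoint and costs little to correct. Its practical reach is narrow: short grade 4 falls in the DLT window that lead to a dose reduction. The effect on DLT incidence and on the MTD cannot be determined from the documents and is zero if no such event occurred.

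A reader might infer that the MTD estimate is wrong, or that a past escalation decision was. The documents do not support either reading. They show no affected event, the dose levels are largely redacted, and the TPI result cannot be recomputed from what is given. The 1/6 to 2/6 illustration rests on one assumed reclassified subject and on Table 1 alone.

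**What to change.** - Reconcile SAP Section 5 with protocol Section 6.2.1.6 so that the DLT listing, incidence table, sensitivity analysis and TPI model all use one stated definition. No view is taken here on which criterion is clinically right.
- State which definition governs subjects whose DLT window preceded amendment 4 (16 July 2018).
- List all grade 4 thrombocytopenia events of 7 days or less that led to a dose reduction, with dates.
- If any subject is classified differently, name the primary definition in advance and show the DLT count and TPI result under the other as a sensitivity analysis. If none is, say so in SAP Section 10.

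The cost is a change of SAP wording, one listing and a check that DLTs are derived for analysis under the stated definition. No new data and no change in sample size are needed.

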6.1 Safety Analysis Set

Safety Analysis Set defined as all subjects that are enrolled and receive at least 1 dose of AMG 224.

6.2 Pharmacokinetic/Pharmacodynamic Analyses Set(s)

6.2.1 Pharmacokinetic Concentration Analyses Set

The PK Analysis Set will contain all subjects who have received at least 1 dose of the investigational product and have at least 1 PK sample collected. These subjects will be evaluated for PK analysis unless the number of data points required for analysis is not enough, or significant protocol deviations have affected the data, or if key dosing or sampling information is missing.

6.3 Dose Limiting Toxicity Evaluable Analysis Set

The analysis of DLT will be restricted to DLT-evaluable subjects. A subject is not DLT-evaluable if he / she discontinues treatment for any reason other than a DLT prior to completing the first 28 days of AMG 224 treatment or does not receive 2 doses of AMG 224 during the 28 day DLT window.

7. Planned Analyses

The Planned analysis is described in following sections.

7.1 Interim Analysis and Early Stopping Guidelines

Safety data will be reviewed on an ongoing basis. **The Dose Level Review Team (DLRT, see protocol Section 10.3.2) will review all available cumulative data by cohort prior to making dose escalation decisions. Adverse events and DLTs observed in all subjects will be evaluated continually and considered in all enrollment and dosing decisions.**

During dose-expansion, the DLRT will review safety after 5 subjects have enrolled (combining Group A and Group B subjects) and completed 28 days on study. A TPI Bayesian model (see protocol Section 10.4.2.3) utilizing all current DLT-evaluable subjects will be fit to evaluate the appropriateness of the preliminary MTD from dose exploration. The subsequent subjects to be enrolled in dose expansion may be dosed with the updated dose level, determined by the DLRT.

Early stopping guidelines will be implemented as explained in the protocol Sections 6.2.1.2-1.4.

7.2 Data Monitoring Committee (DMC), Data Review Team (DRT) or Dose Level Review Team (DLRT)

Dose Level Review Meetings (DLRMs) will be held to review data, monitor safety, and make decisions on dose escalation / change. The DLRT will be composed of the investigators or designees, and the following Amgen representatives: medical monitor, global safety officer or designee, clinical study manager, biostatistician, additional members may be added as needed. The following members are responsible for DLRT decisions: investigators, Amgen medical monitor, and global safety officer or designee. All available study data, including data collected after the initial DLT window, and including demographics, IP administration, medical history, concomitant medications, adverse events, ECGs, vital signs, laboratory data, and PK/PD information will be reviewed. In addition to DLTs, all \geq grade 3 toxicities not meeting DLT criteria will be reviewed and may be considered in DLRT decisions. Modeling of available potential safety risk data (eg, for thrombocytopenia) to predict safety risk for dose escalation decisions may also be considered.

7.3 Primary Analysis

The primary analysis will occur when target enrolment is complete and each subject either completes 6 months on study or withdraws from the study.

7.4 Final Analysis

A final analysis is planned after all dose-exploration cohorts and dose-expansion subjects have ended the study.

8. Data Screening and Acceptance

8.1 General Principles

The objective of the data screening is to assess the quantity, quality, and statistical characteristics of the data relative to the requirements of the planned analyses.

8.2 Data Handling and Electronic Transfer of Data

The Amgen Global Study Operations-Data Management (GSO-DM) department will provide all data to be used in the planned analyses. This study will use the RAVE database.

8.3 Handling of Missing and Incomplete Data

The following imputation for missing or incomplete data will be performed if required:

Incomplete adverse event and concomitant medication dates missing data will be imputed as described in [Appendix A](#).

Non-pharmacokinetic measurements (eg, biomarker data) that are below the lower limit of quantification will be considered equal to half of the lower limit of quantification for all analyses unless specified otherwise.

